##### **10.5.5.2.1 Adverse events (AE)**

All adverse events recorded during study the core study phase and cumulatively reporting core and Extension Phase will be summarized. The incidence of treatment emergent adverse events will be summarized by system organ class, severity (based on CTCAE grades), type of adverse event, relation to the study drug by treatment group. Deaths reportable as SAEs and non-fatal serious adverse events will be listed by patient and tabulated by type of adverse event and treatment group. Adverse events will be summarized by presenting the number and percentage of patients having any adverse event in each body system and having each individual adverse event. Any other information collected (e.g., severity or relatedness to study medication) will be listed as appropriate. In addition, adverse events of related nature may be analyzed by categories regrouping the relevant preferred terms, as appropriate.

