## **8 Safety monitoring and reporting**

### **8.1 Adverse events**

#### **8.1.1 Definitions and reporting**

An adverse event is defined as the appearance of (or worsening of any pre-existing) undesirable sign(s), symptom(s), or medical condition(s) that occur after patient's signed informed consent has been obtained. Please refer to [Section 6.1](#) for the protocol specific definition of study treatment.

Abnormal laboratory values or test results occurring after informed consent constitute adverse events only if they induce clinical signs or symptoms, are considered clinically significant, require therapy (e.g., hematologic abnormality that requires transfusion or hematological stem cell support), or require changes in study medication(s).

Except for screening failures, adverse events that begin or worsen after informed consent should be recorded in the Adverse Events CRF. Conditions that were already present at the time of informed consent should be recorded in the Relevant Medical History/Current Medical Conditions of the patient's CRF. Adverse event monitoring should be continued for at least 28 days following the last dose of study treatment. Adverse events (including lab abnormalities that constitute AEs) should be described using a diagnosis whenever possible, rather than individual underlying signs and symptoms. When a clear diagnosis cannot be identified, each sign or symptom should be reported as a separate Adverse Event. Adverse events will be assessed according to the Common Terminology Criteria for Adverse Events (CTCAE) version 4.0.

If CTCAE grading does not exist for an adverse event, the severity of mild, moderate, severe, and life-threatening, corresponding to Grades 1 - 4, will be used. CTCAE Grade 5 (death) will not be used in this study; rather, information about deaths will be collected through End of Treatment eCRF, Study Evaluation Completion eCRF and/or Survival information.

The occurrence of adverse events should be sought by non-directive questioning of the patient (subject) during the screening process after signing informed consent and at each visit during the study. Adverse events also may be detected when they are volunteered by the patient (subject) during the screening process or between visits, or through physical examination, laboratory test, or other assessments. As far as possible, each adverse event should be evaluated to determine:

1. The severity grade (CTCAE Grade 1-4)

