2. Its duration (Start and end dates or Ongoing at End of Study)
3. Its relationship to the study treatment (Reasonable possibility that AE is related: No, Yes) or  
Its relationship to the study treatment (Reasonable possibility that AE is related: No, Yes, investigational treatment, Yes, the study treatment (non-investigational), Yes, both and/or indistinguishable)
4. Action taken with respect to study or investigational treatment (none, dose adjusted, temporarily interrupted, permanently discontinued, unknown, not applicable)
5. Whether medication or therapy was given (no concomitant medication/non-drug therapy, concomitant medication/non-drug therapy)
6. Whether it is serious, where a serious adverse event (SAE) is defined as in [Section 8.2.1](#).

All adverse events should be treated appropriately. If a concomitant medication or non-drug therapy is given, this action should be recorded on the Adverse Event CRF.

Once an adverse event is detected, it should be followed until its resolution or until it is judged to be permanent, and assessment should be made at each visit (or more frequently, if necessary) of any changes in severity, the suspected relationship to the study treatment, the interventions required to treat it, and the outcome.

Progression of malignancy (including fatal outcomes), if documented by use of appropriate method (for example, as per RECIST 1.0 criteria for solid tumors), should not be reported as a serious adverse event.

Adverse events separate from the progression of malignancy (example, deep vein thrombosis at the time of progression or hemoptysis concurrent with finding of disease progression) will be reported as per usual guidelines used for such events with proper attribution regarding relatedness to the drug.

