## **8.2 Serious adverse events**

### **8.2.1 Definitions**

Serious adverse event (SAE) is defined as one of the following:

- Is fatal or life-threatening
- Results in persistent or significant disability/incapacity
- Constitutes a congenital anomaly/birth defect
- Is medically significant, i.e., defined as an event that jeopardizes the patient or may require medical or surgical intervention to prevent one of the outcomes listed above
- Requires inpatient hospitalization or prolongation of existing hospitalization,
- Note that hospitalizations for the following reasons should not be reported as serious adverse events:
  - Routine treatment or monitoring of the studied indication, not associated with any deterioration in condition
  - Elective or pre-planned treatment for a pre-existing condition that is unrelated to the indication under study and has not worsened since signing the informed consent
  - Social reasons and respite care in the absence of any deterioration in the patient's general condition

Note that treatment on an emergency outpatient basis that does not result in hospital admission and involves an event not fulfilling any of the definitions of a SAE given above is not a serious adverse event

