### **8.2.2 Reporting**

To ensure patient safety, every SAE, regardless of suspected causality, occurring after the patient has provided informed consent and until at least 28 days after the patient has stopped study treatment must be reported to Novartis within 24 hours of learning of its occurrence.

Any SAEs experienced after this 28 days period should only be reported to Novartis if the investigator suspects a causal relationship to the study treatment. Recurrent episodes, complications, or progression of the initial SAE must be reported as follow-up to the original episode within 24 hours of the investigator receiving the follow-up information. An SAE occurring at a different time interval or otherwise considered completely unrelated to a previously reported one should be reported separately as a new event.

Information about all SAEs is collected and recorded on the Serious Adverse Event Report Form; all applicable Sections of the form must be completed in order to provide a clinically thorough report. The investigator must assess and record the relationship of each SAE to each specific study treatment (if there is more than one study treatment), complete the SAE Report Form in English, and send the completed, signed form by fax within 24 hours to the oncology Novartis Chief Medical Office and Patient Safety (CMO&PS) department.

The telephone and telefax number of the contact persons in the local department of CMO&PS, specific to the site, are listed in the investigator folder provided to each site. The original copy of the SAE Report Form and the fax confirmation sheet must be kept with the case report form documentation at the study site.

Follow-up information is sent to the same contact(s) to whom the original SAE Report Form was sent, using a new SAE Report Form stating that this is a follow-up to the previously reported SAE and giving the date of the original report. Each re-occurrence, complication, or progression of the original event should be reported as a follow-up to that event regardless of when it occurs. The follow-up information should describe whether the event has resolved or continues, if and how it was treated, whether the blind was broken or not, and whether the patient continued or withdrew from study participation.

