### **10.1.2 Safety Set**

The Safety Population includes all patients who received at least one dose of study medication and had at least one post-baseline safety assessment.

The safety analysis for the second line will be performed on the subset of patients receiving at least one dose of second line medication. This subset will be referred to as Safety Population 2nd line (Safety 2L). Note: the statement that a patient had no adverse events (on the adverse event eCRF), constitutes a safety assessment.

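### The specified death table leaves out on-treatment deaths from documented progression, and the Safety Set separately excludes dosed patients with no post-baseline safety entry

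*Protocol*

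**What the plan says.** **Deaths in the safety tables.** Protocol Section 10.5.5.2.1: "Deaths reportable as SAEs and non-fatal serious adverse events will be listed by patient and tabulated by type of adverse event and treatment group". No other safety table of deaths is specified.

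**Which deaths are SAEs.** Section 8.2.1 counts an event as serious if it "Is fatal or life-threatening". Section 8.2.2 requires reporting of "every SAE, regardless of suspected causality, occurring after the patient has provided informed consent", until at least 28 days after treatment stops. Section 8.1.1 makes one exception: "Progression of malignancy (including fatal outcomes), if documented by use of appropriate method" (RECIST 1.0 is the example given) "should not be reported as a serious adverse event". The same section asks for events separate from progression to be reported in the usual way.

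**Grading.** Section 8.1.1: "CTCAE Grade 5 (death) will not be used in this study". Instead, "information about deaths will be collected through End of Treatment eCRF, Study Evaluation Completion eCRF and/or Survival information".

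**Population.** Section 10.1.2: the Safety Population "includes all patients who received at least one dose of study medication and had at least one post-baseline safety assessment". A note adds that an entry of no adverse events on the AE page counts as a safety assessment. The second-line subset is described by dosing alone. Section 10.5.5.2 uses the safety population for all safety analyses, limits the summary tables to 28 days after study drug discontinuation, and lists all safety data collected.

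**The concern.** Safety is a stated secondary objective in both lines (Table 3-1). A reader of the safety section expects to see how many patients died on treatment or shortly after, and from what. The death table shows only those deaths that pass an SAE filter, and that filter depends on how the death is classified.

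Classification is not trivial here. Sections 6.2.2.5 and 6.2.2.6 warn of fatal pneumonitis and fatal infection. The trial is open-label (Section 6.3.3), progression is assessed locally (Section 7.2.1), and there is no Data Monitoring Committee (Section 8.5). Every patient entering second line has documented first-line progression (Section 7.1.3). A patient who stops treatment for documented progression also has it on record during the following 28 days. For these patients, whether a death is fatal progression or a separate fatal event rests largely on the investigator's judgement. A table of all deaths by cause would let the reader see that split; the specified table shows only one side of it.

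The Safety Set raises a different issue. Membership depends partly on what is recorded after dosing, so a treated patient who dies or is lost very early could drop out of numerator and denominator alike.

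**Working it through.** There is no planned figure to reproduce. The check follows each kind of on-treatment death through the stated rules.

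| Type of death, first dose to 28 days after last dose | SAE? | In the Section 10.5.5.2.1 death table? | In the AE severity summary? |
|---|---|---|---|
| (a) Assigned to documented progression | No (8.1.1 exception) | No | No Grade 5 entry |
| (b) Fatal adverse event from another cause, toxicity included | Yes (8.2.1, 8.2.2) | Yes | Yes, at most Grade 4 |
| (c) Progression suspected but not documented | Yes; the exception needs documentation | Yes | As (b) |
| (d) Dosed patient, no post-baseline safety entry of any kind | Nothing entered | No; outside the Safety Set | No |

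**Row (a)** follows from the SAE exception and the wording of the death table; the Safety Set plays no part. The death is still on the End of Treatment, Study Evaluation Completion or survival page (8.1.1). Section 14.2.21 requires its reason to be documented, coded and classed as study indication or other. It is covered by the general promise to list safety data (10.5.5.2). It counts in OS on the FAS up to the OS cut-off (10.5.4). The patient also contributes to PFS, subject to the censoring rules of 10.4.3; where progression was documented first, that progression is the PFS event (10.4.1).

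**Row (b)** is a matter of presentation. The fatal event is counted as a death in one table but cannot be told apart from a non-fatal event of the same grade in the severity summary.

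**Row (d)** is narrow. An entry of no adverse events is enough to qualify, and a recorded fatal event should qualify too. Section 7.1.5 calls for safety contact in the 28 days after the last dose even with patients who refuse a final visit. What remains is a patient with nothing entered after dosing, whose death, if any, appears only on a completion or survival page.

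**Overlap of (a) and (d).** This would need progression documented before any post-baseline safety entry. Laboratory and other safety assessments recur at day 1 of Cycle 2, that is after 28 days, while scheduled imaging is every 8 weeks (Table 7-1, Section 7.2.1). Overlap is therefore unlikely.

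**Size.** Denominator: 202 enrolled (Amendment 5 rationale).

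- One omitted death: 1/202 = 0.495%, about 0.5 percentage points.
- The protocol gives no number of such deaths. Assuming 1 to 5: 1/202 = 0.5 points to 5/202 = 2.5 points.
- In second line the denominator is smaller, so each death weighs more, but the number who started second line is not given.

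**The case against.** The strongest reply is that the deaths a safety reader most needs are already covered. Any fatal event other than documented progression is an SAE, reportable whatever its suspected cause, and is tabulated by type of event. The deaths left out are outcomes of the disease, and they are counted under efficacy. Nothing is lost in collection, and not using Grade 5 is a convention backed by dedicated death pages. An all-deaths table is ordinary SAP content, and the SAP is not at hand.

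Most of this stands, and it rules out three stronger readings that a reader might infer:

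- **That the rules combine to make a death vanish.** They do not. The death-table gap and the Safety Set condition are separate routes, and the deaths in row (a) remain in the listings and in OS.
- **That toxic deaths are hidden.** They are SAEs and reach the death table.
- **That the investigator's opinion alone exempts a death.** The exception requires documented progression.

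The reply does not remove two points. The protocol does not leave the death table open for the SAP to define; it states a rule, and that rule restricts the table to SAE-reportable deaths. The post-baseline condition is likewise stated, and it would remain even if the SAP had an all-deaths table.

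**Conclusion.** The point holds in a limited form. As written, an on-treatment death assigned to documented progression appears in no safety table the protocol specifies, and fatal adverse events are not distinguishable in the severity summary. Separately, the first-line Safety Set carries an unnecessary condition that can remove a dosed patient. The primary PFS analysis is unaffected.

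The size cannot be fixed from the protocol: about 0.5 percentage points per affected death, and 0.5 to 2.5 points under the assumption of 1 to 5 such deaths among 202. The Safety Set route probably affects very few patients or none. The conclusion rests on reading the documentation condition in Section 8.1.1 literally and on treating a recorded fatal event as a post-baseline safety assessment. If the SAP already tabulates all deaths by cause, the first part reduces to aligning the protocol wording with it.

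**What to change.** 1. **Section 10.1.2:** define the Safety Set as all patients who received at least one dose of study medication, dropping the post-baseline condition. The second-line subset is already described by dosing alone and needs no change in substance.
2. **Section 10.5.5.2.1:** keep the table of SAE deaths and add one of all deaths from first dose to 28 days after last dose, by line of treatment and primary cause (study indication or other), whatever their SAE status.
3. **Severity summary:** flag adverse events with a fatal outcome. Grade 5 need not be introduced.

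The cost is one extra table and some wording, using data already on the completion and survival pages. The reported number of deaths can only stay the same or rise, so the safety figures may look slightly less favourable.

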##### **10.5.5.2.2 Laboratory abnormalities**

All laboratory values collected during the core study phase will be converted into SI units and the severity grade calculated using appropriate common toxicity criteria (CTCAE). A listing of laboratory values will be provided by laboratory parameter, patient, and treatment group. A separate listing will display notable laboratory abnormalities (i.e., newly occurring CTCAE grade 3 or 4 laboratory toxicities). The frequency of laboratory abnormalities will be displayed by parameter and treatment group.

Laboratory data will be classified into CTC grades according to the NCI Common Terminology Criteria for Adverse Events (CTCAE) v4.0. A severity grade of 0 will be assigned when the value is within normal limits. In the unlikely case when a laboratory

normal range overlaps into the higher (i.e. non-zero) CTC grade, the laboratory value will still be taken as within normal limits and assigned a CTC grade of zero. Besides listings, the following summaries will be produced for the laboratory data (by laboratory parameter and treatment):

- Number and percentage of patients with worst post-baseline CTC grade (regardless of the baseline status). Each patient will be counted only for the worst grade observed post baseline.
- Shift tables using CTC grades to compare baseline to the worst post-baseline value will be produced for hematology and biochemistry laboratory parameters with CTC grades. For laboratory parameters where CTC grades are not defined, shift tables to the worst post baseline value will be produced using the low/normal/high classifications based on laboratory reference ranges.

#### 10.5.5.2.3 Other safety data

Data from other tests (e.g. vital signs) collected during the Core Phase will be listed, notable values will be flagged, and any other information collected will be listed as appropriate. Any statistical tests performed to explore the data will be used only to highlight any interesting comparisons that may warrant further consideration.

#### 10.5.5.3 Extension Phase

The secondary objective related to the Extension Phase of the study is to evaluate clinical benefit as assessed by the Investigator. Proportion of patients with clinical benefit as assessed by the Investigator will be summarized at scheduled visits.

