**Table 3-1 Objectives and related endpoints**

Objective	Endpoint	Analysis
Primary: The primary objective is to estimate progression-free survival in patients treated with everolimus + letrozole in the first line setting.	PFS	Refer to Section 10.4 .
Secondary: Determine the overall response rate and clinical benefit rate of everolimus + letrozole in the first line setting	ORR, CBR	Refer to Section 10.5.1 .
Determine the progression free survival, overall response rate and clinical benefit rate of everolimus + exemestane in second line population	PFS, ORR, CBR	Refer to Section 10.5.2 and Section 10.5.3 .
Evaluate the safety of everolimus + letrozole in the first line setting	Incidence of Adverse events	Refer to Section 10.5.5.2 .
Evaluate the safety of everolimus + exemestane in the second line setting	Incidence of Adverse events	Refer to Section 10.5.5.2 .
Estimate the overall survival of patients treated with everolimus + letrozole in the first line setting	OS	Refer to Section 10.5.4 .
Evaluate a therapeutic intervention to reduce the severity and duration of stomatitis	Oral Stomatitis Daily Questionnaire (OSDQ) data	Refer to Section 10.5.5.1 .
Evaluate clinical benefit as assessed by the Investigator during the Extension Phase	Proportion of patients with clinical benefit as assessed by the Investigator at scheduled visits	Refer to Section 10.5.5.3 .
Evaluate long term safety data	Frequency and severity of AEs/SAEs	Refer to Section 10.5.5.2 .

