### **7.1.3 Second line treatment**

Following disease progression in the first line setting, patients will be offered everolimus in combination with exemestane during the Core Phase, during the Extension Phase these patients will be discontinued from the study. Patients who discontinued first line treatment due to reasons other than disease progression are not eligible for second line treatment.

Informed consent will not be repeated for patients moving into the second line treatment period. However, specified inclusion / exclusion criteria must be re-examined (see [Section 5.1](#)) and collected on the eCRF.

At the determination of documented disease progression (e.g., image scan that determined the disease progression) in the first line treatment, the patient must begin second line treatment within 28 days.

A complete schedule of evaluations required for the second line treatment period are provided in [Table 7-2](#).

The procedures for patients receiving second line treatment will proceed as follows:

- Re-examination of specified inclusion/exclusion criteria, see [Section 5.1](#).
- ECOG Status
- Current concomitant medications
- Safety laboratory assessments: chemistry, hematology, urinalysis, coagulation
- HBV and HCV testing and monitoring should be continued only for those patients identified during enrollment on first line treatment. Testing should be performed as per [Section 6.2.2.3](#).
- Tumor evaluations will follow the same schedule used in the first line treatment period. If the end of treatment tumor evaluations from the first line treatment period that lead to documentation of disease progression is <28 days prior to starting the second line treatment medication, then the end of treatment tumor evaluations from the first line will serve as Cycle 101 day 1 tumor evaluations for second line treatment period

- All continuing concomitant medications from the first line treatment period will be followed into the second line treatment period and will be recorded on the Concomitant Medications eCRF
- Treatment with everolimus and exemestane in the second line period continues until documented disease progression or any other reason for which the patient may be discontinued (refer to [Section 7.1.5](#))

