#### **7.1.4 Extension Phase**

Following the overall survival cut-off (24 months post LPFV) and approval of Amendment 5, patients continuing to derive benefit from everolimus will be transitioned to an Extension Phase until disease progression or any other reason for which the patient may be discontinued (refer to [Section 7.1.5](#)).

Patients will be re-consented prior to starting the Extension Phase.

Patients must return to the study center on a quarterly basis (12 weeks  $\pm$  1 week) for resupply of medication at which time drug dispensing information and adverse event information will be collected.

A complete schedule of evaluations required for the Extension Phase is provided in [Table 7-3](#).

The procedures for patients entering the Extension Phase will proceed as follows:

- Safety laboratory assessments: chemistry, hematology, urinalysis, coagulation will be done as clinically indicated
- HBV and HCV testing and monitoring should be continued only for those patients identified during enrollment on first line treatment. Testing should be performed as per [Section 6.2.2.3](#).
- Treatment with everolimus and letrozole (1st line) or everolimus and exemestane (2nd line) until lack of clinical benefit as assessed by Investigator at the site or any other reason for which the patient may be discontinued (refer to [Section 7.1.5](#)) Patients entering the Extension Phase on 1st line treatment and deemed to no longer be clinically benefiting will not be offered 2nd line treatment in the context of this study)
- At every quarterly visit, the investigator is required to confirm that the patient continues to have clinical benefit and may continue receiving study treatment. Although formal assessment of efficacy is not required during the Extension Phase, confirmation of continued treatment benefit as per standard of care is mandatory.
- When patients discontinue the first or second line treatment for any reason, an end of treatment visit following discontinuation of the medication will be performed. The 28 day follow up visit will also be performed to check on continuing AEs/SAEs or any new AEs/SAEs that may have occurred

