#### **7.1.6.2 Survival follow up**

All patients who discontinued study treatment, have started a new antineoplastic therapy, and/or are no longer followed radiologically will be contacted (via telephone) for survival information every 12 weeks from the patient's last visit (which can be the safety follow up visit), until death, lost to follow up or withdrawal of consent. The investigator or his designee will collect this survival information and any additional antineoplastic therapies for all patients until the final survival analysis.

Patients who withdraw consent from participation in study should be asked to consent for survival follow up. If applicable, information regarding the death should be captured in the eCRF.

Patients completing the Extension Phase will not be followed for survival.

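### The Extension Phase benefit proportion has no stated denominator; taken over the patients assessed at each visit, it hides cumulative loss of benefit

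*Protocol*

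**What the plan says.** Section 10.5.5.3 gives the whole analysis in one sentence: "Proportion of patients with clinical benefit as assessed by the Investigator will be summarized at scheduled visits". Table 3-1 lists the endpoint as "Proportion of patients with clinical benefit as assessed by the Investigator at scheduled visits". Neither states who is in the denominator, or how a patient who has left is counted at later visits. Section 10.1 defines no analysis set for the Extension Phase.

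The rules for entering, staying and leaving are in section 7.1.4 and nearby:

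- **Entry:** "patients continuing to derive benefit from everolimus will be transitioned to an Extension Phase".
- **Staying:** "At every quarterly visit, the investigator is required to confirm that the patient continues to have clinical benefit and may continue receiving study treatment".
- **Leaving:** treatment runs "until lack of clinical benefit as assessed by Investigator at the site or any other reason for which the patient may be discontinued". For patients who progress on first-line treatment, section 7.1.3 says that "during the Extension Phase these patients will be discontinued from the study".
- **Afterwards:** "Patients completing the Extension Phase will not be followed for survival" (section 7.1.6.2).

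Section 7.2.1 confirms that the physician's benefit judgement is the only efficacy assessment in this phase.

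**The concern.** The judgement that forms the endpoint also decides who remains under observation. Everyone has benefit at entry by selection. A patient judged to have lost it stops treatment and, after the end-of-treatment and 28-day safety visits, has no further scheduled visit at which she could be counted as without benefit. On the ordinary reading of a by-visit proportion, where the denominator is the patients assessed at that visit, each figure is conditioned on benefit having lasted until the previous visit.

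Two extensions with very different durability could then produce similar tables. A reader who sees around 85% or 90% at the last visit could take it as the share of entrants who kept benefit for three years, when it is the share of the few remaining patients who kept it over the last 12 weeks.

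**Working it through.** The protocol states no figure for this endpoint, so there is none to reproduce. The check compares what the planned summary would show under different denominators.

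**Inputs**

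- Visit interval: 12 weeks (7.1.4 and Table 7-3), that is 84 / 30.44 = 2.76 months.
- Length: up to 3 years (4.1), that is 156 / 12 = 13 intervals.
- Size: 64 first-line and 19 second-line patients were ongoing at the June 2016 cut-off (Amendment 5 rationale). Enrolment was closed, so 64 + 19 = 83 is a rough ceiling for the number of entrants.
- Time to loss of benefit: not given. **Assumption:** exponential, with medians from 6 to 36 months.

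**Formulas.** Let q = exp(−ln 2 × 2.76 / median), the chance of keeping benefit over one interval.

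- A: denominator is patients assessed at the visit, and every loss is recorded as a no at a scheduled visit. The proportion is q at each visit after entry.
- B: same denominator, but losses are found between visits and appear only at end of treatment. The proportion is 1.
- C: denominator is all entrants. The proportion is q^k at the k-th visit after entry.

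For a 12-month median, q = exp(−0.693 × 2.76 / 12) = 0.853, and q^4 = 0.529, q^8 = 0.279, q^13 = 0.126.

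| Assumed median (months) | A, any visit | B, any visit | C, week 12 | C, week 48 | C, week 96 | C, week 156 |
|---|---|---|---|---|---|---|
| 6 | 0.727 | 1.00 | 0.727 | 0.279 | 0.078 | 0.016 |
| 12 | 0.853 | 1.00 | 0.853 | 0.529 | 0.279 | 0.126 |
| 24 | 0.923 | 1.00 | 0.923 | 0.727 | 0.529 | 0.355 |
| 36 | 0.948 | 1.00 | 0.948 | 0.809 | 0.654 | 0.501 |

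If half the losses are recorded at a visit and half between visits, the visit-based figure is q / (q + 0.5(1 − q)): 0.84, 0.92 and 0.96 for medians of 6, 12 and 24 months.

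**In patients.** With 83 entrants and a 12-month median, 83 × 0.529 = 44 keep benefit at week 48 and 83 × 0.126 = 10 at week 156. Under A or B the table would still show 0.85 to 1.00 at both visits.

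**Sensitivity to durability.** Doubling the median from 12 to 24 months moves A from 0.853 to 0.923. It moves C at week 156 from 0.126 to 0.355.

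**Sensitivity to the exponential assumption.** With a rising rate of loss (Weibull, shape 2, median 12 months), A is no longer flat: it is 0.964 at week 12, 0.774 at week 48 and 0.577 at week 96. C falls much further, to 0.556 at week 48 and 0.096 at week 96.

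**The case against.** A reader might infer that the proportion is high by construction and cannot show loss of benefit. The protocol does not support that, for three reasons.

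- The denominator is left open. With all entrants in it, the same sentence in 10.5.5.3 yields a declining, informative figure. The protocol uses whole analysis sets for its response and clinical benefit rates (10.5.1 and 10.5.3), and a statistical analysis plan, not at hand here, may do likewise.
- Even among patients assessed, a no at the visit where loss is found counts once. The figure is then one minus the interval loss rate. It varies with durability (0.73 to 0.95 for medians of 6 to 36 months) and falls over time if the rate of loss rises. The flat line comes from the exponential assumption, not from the design.
- Losses between visits are not lost to the data. Section 7.1.5 requires an end-of-treatment visit and a separate Extension Phase end-of-treatment form with the date and reason for stopping.

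It can be added that section 10.3.1 summarises treatment exposure in the extension, which bears on durability; that Amendment 5 gives safety monitoring and access to treatment as the purpose of the phase; and that the stated objective speaks of evaluating benefit, not its duration.

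These points limit the concern but do not remove it. The protocol does fix the form of the summary, a per-visit proportion, and on its ordinary reading that form misleads. Exposure duration mixes loss of benefit with every other reason for stopping, so it is no substitute. The dates and reasons are collected, but the planned summary does not use them.

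**Conclusion.** The point holds in a limited form. The denominator is not stated, and if it is the patients assessed at each visit, the summary is conditioned on continuing benefit and hides cumulative loss. It does not hide all loss: the most recent interval still shows, in so far as losses are recorded at scheduled visits. Nor does the text force this denominator.

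Under an assumed 12-month exponential median, the gap at week 48 is 85% to 100% against 53% of entrants, and at week 156 it is 85% to 100% against 13%. A longer median narrows the gap: at 36 months it is 95% to 100% against 50% at week 156. All these percentages rest on assumed medians; only the visit interval, the length and the approximate number of entrants come from the protocol.

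This is a descriptive secondary endpoint with no hypothesis test. The primary progression-free survival analysis and the other Core Phase results are unaffected. The change should be made because this is the only efficacy summary of the phase.

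**What to change.** In section 10.5.5.3 and Table 3-1, report a Kaplan-Meier estimate of time from Extension Phase entry to loss of benefit, by line of treatment. Define loss as investigator-judged lack of benefit, progression or death, whichever comes first. Censor patients who leave while still benefiting: three years completed, administrative end, or discontinuation of development by the sponsor. State how toxicity stops and consent withdrawals are handled; counting them all as loss of benefit is debatable, so the rule should be explicit.

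Alternatively or in addition, give at each scheduled visit the number with benefit over all Extension Phase entrants, with the reasons for leaving shown beside it.

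The inputs are the quarterly benefit confirmation and the dates and reasons on the Extension Phase end-of-treatment form, so no new data are needed. The reasons listed in section 7.1.5 include progression and death but have no separate entry for lack of benefit, so the definition should say how the visit judgement and the form are combined. The cost is a few sentences in the analysis section and a lower reported percentage.
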